4.8. Guidelines for Events of Special Interest and Dose Modifications

The severity of adverse events (AEs) will be graded utilizing the National Cancer Institute- Common Toxicity Criteria for Adverse Events (NCI-CTCAE), version v4.03. Guidelines for dose modifications and interruptions for management of common toxicities associated with the study treatment(s) are provided in this section.

4.8.1. Events of Special Interest

Any signs of bleeding, bruising and infection will be monitored closely throughout the study. Platelet transfusion will be administered following institutional guidelines and practices. Neutropenia and anemia management and fungal or bacterial prophylaxis will also follow institutional guidelines.

4.8.2. Dose Adjustment for Non-Hematologic Toxicity

See [Table 2](#) Dose Adjustment Guideline for drug related non-hematologic toxicities based on worst grade.

Table 2 Dose Adjustment Guideline for Drug Related Non-Hematologic Toxicity

Worst Grade	Dose Adjustment
G1	No change in dose
G2 [†]	Continue dosing with no change OR Consider holding for up to 2 weeks for toxicity to resolve to baseline or ≤ Grade 1, then continue at the same dose OR dose reduce by at least 25% if the toxicity is considered a DLT.
G3 and 4 [†]	Hold for up to 2 weeks for toxicity to resolve to baseline or ≤ Grade 1, then dose reduce by at least 25%. If no recovery to ≤Grade 1* or baseline after 14 days, patient should be withdrawn.

*Note: Exceptions to ≤ drug-related Grade 1 requirement may be made for rash, alopecia, quickly reversible (<72 hours) laboratory abnormality (example: electrolyte changes).

[†]In combination cohort, consider holding ATRA dosing first for skin related toxicity (dryness, rash), nausea, vomiting, pain, headache, and mucositis. With fever, consider holding LSD1 first to allow neutrophil count to recover.

If the non-hematologic toxicity or event resolves to baseline or ≤ Grade 1 within 14 days of stopping therapy, treatment with GSK2879552 and/or ATRA may be restarted with at least **25%** dose reduction. For a non-DLT, the treatment with GSK2879552 could restart at a full dose, if deemed appropriate.

If the non-hematologic toxicity does not resolve to ≤ Grade 1 or baseline within 14 days, the subject should be withdrawn from the treatment permanently (Section 6.3). However, if the investigator and GSK Medical Monitor agree that further treatment will benefit the subject, treatment can restart with at least **25%** dose reduction once the toxicity resolves to ≤ Grade 1 or baseline.

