4.2.5. Dose-Limiting Toxicity

An event will be considered a DLT if it occurs within the first 28 days of treatment (with exception of myelosuppression as stated below), and meets one of the following criteria unless it can be clearly established that the event is unrelated to treatment.

Subjects unable to receive at least 75% of scheduled doses within the DLT period for reasons other than toxicity (e.g., acute illness, disease progression) will not be evaluable

- Hematologic DLT: Myelosuppression (as defined by absolute neutrophil count (ANC) $<500/\mu\text{l}$ AND platelets $\leq 25,000/\mu\text{l}$) with bone marrow hypoplasia (cellularity $\leq 5\%$) without evidence of leukemia ($<5\%$ blasts) for ≥ 42 days after drug cessation.
- Grade ≥ 3 non-hematologic toxicity that is considered clinically significant and lasts >72 hours. Fatigue, asthenia, or nausea that respond to standard medical care within 72 hours and new electrolyte disturbance that respond within 24 hours are exceptions. In addition, electrolyte disturbances associated with underlying malignancy are not considered DLT.
- Grade 2 toxicity that in the judgment of the investigator and GSK Medical Monitor is dose-limiting.
- Treatment delay of ≥ 42 days due to unresolved toxicity (without evidence of leukemia ($<5\%$ blasts)).

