6.3. Permanent Discontinuation from Study Treatment

Subjects will receive study treatment until disease progression, death or unacceptable toxicity, including meeting stopping criteria for liver chemistry defined in Section 4.7.1. The investigator may discuss with a GSK Medical Monitor continuing a subject who is receiving benefit but has met the criteria for disease progression, if the following criteria are met: Investigator-determined clinical benefit (e.g. symptomatic improvement), lack of

significant toxicity (no drug related non-hematologic grade 3/4 AEs within the last 4 weeks) and no therapeutic alternatives expected to provide durable responses.

In addition, study treatment may be permanently discontinued for any of the following reasons:

- Deviation(s) from the protocol
- Request of the subject or proxy (withdrawal of consent by subject or proxy)
- Investigator's discretion
- A clinically significant hematologic adverse event leading to an interruption of treatment for greater than 28 days. Subjects will be allowed up to a 28-day delay in dosing for hematologic toxicity to resolve or for scheduling difficulties. If the investigator and GSK Medical Monitor conclude that the benefit: risk supports continued treatment of a subject who has had a > 28 day treatment delay, then the subject may continue therapy with the approval of the GSK Medical Monitor.
- A clinically significant non-hematologic adverse event leading to an interruption of treatment for greater than 14 days. Subjects will be allowed up to a 14-day delay in dosing for non-hematologic toxicity to resolve or for scheduling difficulties. If the investigator and GSK Medical Monitor conclude that the benefit: risk supports continued treatment of a subject who has had a > 14 day treatment delay, then the subject may continue therapy with the approval of the GSK Medical Monitor.
- Persistent G4 thrombocytopenia for 4 weeks not attributed to disease or requires platelet transfusions for bleeding in the absence of the disease.
- Intercurrent illness that prevents further administration of study treatment(s)
- Subject is lost to follow-up
- Study is closed or terminated.

The primary reason study treatment was permanently discontinued must be documented in the subject's medical records and electronic case report form (eCRF).

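### Section 4.8.2 gives two restart rules for the same Grade 3-4 non-hematologic event: Table 2 requires a dose reduction, but the text below it can be read to allow full dose for any non-DLT

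*Protocol*

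**What the plan says.** Protocol Section 4.8.2 covers drug-related non-hematologic toxicity in a table and in text below it.

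- **Table 2, Grade 3 and 4 row:** "Hold for up to 2 weeks for toxicity to resolve to baseline or ≤ Grade 1, then dose reduce by at least 25" percent. No DLT condition is attached.
- **Table 2, Grade 2 row:** dosing may continue, or be held and resumed at the same dose. A reduction of at least 25% applies only if the event counts as a DLT.
- **First paragraph below the table:** if toxicity of any grade resolves "within 14 days of stopping therapy, treatment with GSK2879552 and/or ATRA may be restarted with at least" a 25% reduction. It then adds: "For a non-DLT, the treatment with GSK2879552 could restart at a full dose, if deemed appropriate". This second sentence concerns GSK2879552 only and names no decision-maker.
- **Next paragraph, slower recovery:** the default is withdrawal. "However, if the investigator and GSK Medical Monitor agree that further treatment will benefit the subject, treatment can restart with at least" a 25% reduction, once the toxicity has resolved. DLT status plays no part.

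DLT status is defined in Section 4.2.5: "An event will be considered a DLT if it occurs within the first 28 days of treatment", with an exception only for myelosuppression. The criteria relevant here are Grade 3 or higher "non-hematologic toxicity that is considered clinically significant and lasts >72 hours", with stated exceptions, and "Grade 2 toxicity that in the judgment of the investigator and GSK Medical Monitor is dose-limiting".

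**The concern.** The 28-day window exists to support dose escalation and the MTD definition in Section 4.2.6. If it also decides who may go back to full dose, two subjects with the same severe event can be handled differently only because of the day it began. Treatment continues past Day 28 until progression, unacceptable toxicity or withdrawal of consent (Section 4.1), so late events are possible.

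The table and the text also differ. A site working from Table 2 would reduce after every related Grade 3-4 event, while a site working from the paragraph could resume at full dose. At stake is re-exposure to the dose that preceded a severe toxicity, and uneven handling of the same event across sites.

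**Working it through.** The plan states no figure on this point, so the check sets the provisions side by side.

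**Scope.** Related Grade 3-4 non-hematologic events for which GSK2879552 is held, that resolve to baseline or Grade 1 or less within 14 days, and that have no rule of their own. This leaves out liver chemistry (4.7.1), QTc (4.7.2), mental status (4.7.3), bleeding, fever or sepsis with low platelets (4.8.3), retinoic acid syndrome, ALT elevation on ATRA and pseudotumor cerebri (4.8.4), and combination-arm events where only ATRA is held.

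**Step 1: does the Grade 3-4 row contain an exception?** No. One footnote to Table 2 relaxes the recovery requirement for a few event types, and the other says which drug to hold first in the combination. Neither removes the reduction.

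**Step 2: which in-scope events are non-DLTs under 4.2.5?**
- Onset from Day 29: all of them, because the window has closed. The 42-day treatment-delay criterion cannot apply to an event that resolves within 14 days.
- Onset in Days 1-28: those lasting 72 hours or less, those not considered clinically significant, and those under the listed fatigue, asthenia, nausea and electrolyte exceptions.

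**Step 3: compare the restart doses.** The example is 20 mg monotherapy, a dose level in SAP Section 5.1, with related Grade 3 diarrhea that is clinically significant. Days and durations are illustrative. Highest dose after a 25% reduction: 20 × 0.75 = 15 mg. Ratio: 20 / 15 = 1.33.

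| Event | DLT? | Table 2 row | Paragraph, read literally |
|---|---|---|---|
| Onset Day 20, lasts 10 days | Yes | 15 mg or less | 15 mg or less |
| Onset Day 29, lasts 10 days | No | 15 mg or less | 20 mg permitted |
| Onset Day 10, lasts 2 days | No | 15 mg or less | 20 mg permitted |

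The texts agree in the first row and conflict in the other two.

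**Step 4: how much dosing falls after Day 28?** Treatment duration is not given, so it is assumed. Share of treatment days = (days − 28) / days:
- 4 weeks: 0%
- 8 weeks: (56 − 28)/56 = 50%
- 12 weeks: (84 − 28)/84 = 67%
- 24 weeks: (168 − 28)/168 = 83%

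These are shares of days, not of events. Section 1.4.2 cites a median survival of 4 months in refractory AML, so the longest assumption is generous for such patients.

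**The case against.** The strongest reply is that no conflict exists. Only the Grade 2 row depends on DLT status, so the full-dose sentence may simply restate that row. On that reading no Grade 3-4 event qualifies on any day. This is tenable, but the text does not secure it. The paragraph opens with toxicity of any grade, the sentence follows the 25% reduction as an exception to it, and a Grade 2-only sentence would add little to what the row already allows. The protocol does not say which text governs.

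A reader might infer the stronger claim that 4.8.2 settles the matter and permits full-dose restart for every severe event from Day 29. The documents do not support that, because the Grade 3-4 row says the opposite without qualification. Nor is Day 29 the only boundary, as Step 2 shows.

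Two comparisons also look more telling than they are. The stricter rule for recovery beyond 14 days may simply reflect slow recovery. Section 6.3 asks for "no drug related non-hematologic grade 3/4 AEs within the last 4 weeks", but that is a condition for treatment beyond progression and does not address restart dose.

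Safeguards remain. Section 4.8 is framed as guidelines, recovery must come first, full dose is optional, Section 4.1 allows reduction for recurrent or persistent toxicity, and Section 6.3 ends treatment for unacceptable toxicity. These lower the severity but do not remove the mismatch.

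**Conclusion.** The point holds as an internal inconsistency. For in-scope Grade 3-4 events, Table 2 requires a reduction of at least 25%, while the paragraph beneath can be read to allow full dose for any non-DLT. On that literal reading, late events of any severity qualify, as do brief or non-significant ones in the first 28 days. The difference at 20 mg is 20 mg against 15 mg or less, or 33% above the highest reduced dose.

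This rests on the wording of 4.8.2 and 4.2.5 alone. The documents do not give the number of affected events, no harm is shown, and clinical judgment applies on either reading, so the severity is modest. SAP Section 2.1 records that the study ended early, before Part 2 began. The point therefore concerns the protocol as written.

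**What to change.** Leave the Table 2 Grade 3-4 row as it is. In the paragraph below, replace the opening words *For a non-DLT* with *For a Grade 2 event not judged dose-limiting, regardless of study day*, and keep the rest of the sentence. The text then matches both rows and no longer depends on the 28-day window.

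At minimum, replace those words with *For an event that would not meet any Section 4.2.5 non-hematologic DLT criterion if the 28-day window were disregarded*. This is second best. It closes the late-onset gap but leaves brief or non-significant Grade 3-4 events in conflict with the row.

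Do not reconcile the two by adding a full-dose exception to the Grade 3-4 row, which would loosen the stricter existing rule.

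The cost is one clause, with no added data or procedures. The downside is slightly less investigator discretion, mainly for Grade 3-4 events that some sites might otherwise have restarted at full dose.

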4.8.3. Dose Adjustment For Hematologic Toxicity

Toxicity	Dose Adjustment/ Stopping Criteria	Management Guidelines
At all thrombocytopenia grades, implement fall precautions to avoid bleeding due to trauma, e.g. trauma to head can cause a subdural hematoma. This risk increases with higher grades of thrombocytopenia		
Thrombocytopenia regardless of blast count	Grade 1, 2 & 3 (platelets $\geq 25,000/\text{mm}^3$)	Continue dosing at same dose level with more frequent monitoring as necessary.
Thrombocytopenia if blasts >5%	Grade 4 (platelets $< 25,000/\text{mm}^3$) and/or any grade accompanied by severe bleeding related to thrombocytopenia	
If platelet count $< 25,000/\text{mm}^3$ but $\geq 10,000/\text{mm}^3$:
 
 1. Use clinical judgement to institute more frequent monitoring as necessary 2. Institute platelet transfusion as appropriate. 
If platelet count $< 10,000/\text{mm}^3$:
 
 1. Continue treatment and start platelet transfusion as per institutional guidelines. 2. If repeat platelet transfusions are not able to rescue platelet count, then consider irradiated, leukapherised or HLA-matched platelets as clinically appropriate 3. If still unable to rescue platelet count, investigator may consider treatment interruption in discussion with medical monitor. 4. Use of concomitant therapies (tranexamic acid) is permitted. Please note tranexamic acid is prohibited for subjects receiving GSK2879552 in combination with ATRA. 5. Use of hydroxyurea in the setting of increased blast counts in conjunction with decreased platelet counts is permitted.
Thrombocytopenia if blasts <5%	Grade 4 (platelets $< 25,000/\text{mm}^3$) and/or any grade accompanied by severe bleeding related to thrombocytopenia	
If platelet count $< 25,000/\text{mm}^3$ but $\geq 10,000/\text{mm}^3$:
 
 1. Use clinical judgement to institute more frequent monitoring as necessary 2. Institute platelet transfusion as appropriate. 
If platelet count $< 10,000/\text{mm}^3$ (or $\leq 25,000/\text{mm}^3$ with accompanying fever, sepsis, or minor bleeding):
 
 1. Treatment may be held for up to 4 weeks and resume* as soon as count recovery has occurred (i.e., neutrophils ≥ 0.5 and platelets $\geq 25 \times 10^9/\text{L}$). Use clinical judgement to institute more frequent monitoring as necessary. 2. The treatment may be held for additional 1-2 weeks if the neutrophil and platelet counts do not recover after the initial 2 weeks. 3. After a total of 5-6 consecutive weeks, if there is no evidence of recovering blood counts, a repeat bone marrow examination should be performed

Toxicity	Dose Adjustment/ Stopping Criteria	Management Guidelines
		
during that period (approximately -35-42 days after drug cessation) to evaluate for the possibility of hematologic DLT.
 
4. If persistent for 6 weeks and not attributed to disease or requires platelet transfusions for bleeding in the absence of the disease, the subject will be withdrawn from the study.
 
*If treatment resumes, the dose and schedule may be adjusted based on platelet count, i.e., dose can be reduced by at least 25% increments up to two times.

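### Protocol 4.8.3 starts the extra 1–2 week hold from an initial 2 weeks; only an initial 4 weeks yields the 5–6 weeks that the same row states

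*Protocol*

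**What the plan says.** The row in Protocol 4.8.3 for blasts below 5% applies its hold sequence to subjects with platelets under 10,000/mm3, or at or below 25,000/mm3 "with accompanying fever, sepsis, or minor bleeding". The sequence has four items:

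- Item 1: "Treatment may be held for up to 4 weeks", with treatment resuming once counts recover.
- Item 2: "The treatment may be held for additional 1-2 weeks if the neutrophil and platelet counts do not recover after the initial 2 weeks".
- Item 3: "After a total of 5-6 consecutive weeks, if there is no evidence of recovering blood counts", the marrow is repeated, at about "35-42 days after drug cessation", to look for a hematologic DLT.
- Item 4: "If persistent for 6 weeks and not attributed to disease", the subject is withdrawn. Need for platelet transfusion for bleeding without disease has the same result.

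Protocol 4.2.5 uses 42 days twice: as the duration of myelosuppression after drug cessation that makes a hematologic DLT, and as the treatment delay that is itself a DLT.

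Protocol 6.3 states that "study treatment may be permanently discontinued for any of the following reasons", and its list includes "Persistent G4 thrombocytopenia for 4 weeks not attributed to disease". It allows a 28-day delay for hematologic toxicity and requires Medical Monitor approval for a subject to continue therapy after a longer one. Section 4.8.3 does not cite 6.3, although 4.8.2 does for non-hematologic toxicity.

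**The concern.** The four items form one sequence, and each should start where the previous one ends. Item 2 does not. It extends a hold whose initial length it takes as 2 weeks, directly after item 1 has set that length at up to 4. A site that follows item 2 literally has an extension that ends no later than the hold it is meant to extend, and then meets an item 3 that assumes a hold of 5–6 weeks.

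The row governs how long a subject with severe cytopenia stays off drug and when the marrow that informs a hematologic DLT is taken. Thrombocytopenia is the drug's primary toxicity (Protocol 1.4.5.1), and treatment-related Grade 4 cases had already been reported (Protocol 1.3.5), so sites can expect to use this row.

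**Working it through.** **Inputs**

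- Initial hold: up to 4 weeks = 28 days (4.8.3, item 1); 2 weeks = 14 days (item 2).
- Extension: 1–2 weeks = 7–14 days (item 2).
- Stated total: 5–6 weeks (item 3); limit of 6 weeks (item 4).
- DLT duration and delay: at least 42 days (4.2.5, both criteria).

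**Formula:** end of hold = initial hold + extension.

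**Step 1. The plan's own figure.** Item 3 gives 5 × 7 = 35 to 6 × 7 = 42 days, which agrees with its own day range. An initial 4 weeks reproduces it: 28 + 7 = 35 and 28 + 14 = 42. The upper end equals the 6-week limit in item 4 (6 × 7 = 42) and the 42 days in 4.2.5.

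**Step 2. Item 2 as written.** From an initial 2 weeks: 14 + 7 = 21 and 14 + 14 = 28 days. The later end is the 28 days that item 1 already allows, so the extension adds 28 − 28 = 0 days. Against item 3 the shortfall is 35 − 21 = 14 days at the lower end and 42 − 28 = 14 days at the upper end.

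| Initial hold | End of extension | Agrees with items 3 and 4 and with 4.2.5? |
|---|---|---|
| 2 weeks (item 2) | days 21–28 | No |
| 4 weeks (item 1) | days 35–42 | Yes |

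**Step 3. 4.8.3 beside 6.3.** At 4 weeks 6.3 permits discontinuation; at 6 weeks 4.8.3 requires withdrawal. The interval is 42 − 28 = 14 days. A site can comply with both, because an option at one time and an obligation at a later time do not conflict.

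**Step 4. The DLT marrow after a permanent stop.** Item 3 and the hematologic DLT in 4.2.5 both count from drug cessation, and neither limits that term to a temporary hold. If a subject is permanently discontinued on day 28 of a hold, the marrow is due 35 − 28 = 7 to 42 − 28 = 14 days later. Table 3 in 7.1 shows no disease-assessment marrow at end of treatment, and the aspirates it does show there are optional at progression. An empty cell in a visit schedule does not cancel an event-driven examination required elsewhere.

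**The case against.** The best defence is that this is a one-figure slip which its own row corrects. Items 1, 3 and 4 all point to a hold that may reach 6 weeks, and a careful reader would arrive there. Week 2 could also be meant as a checkpoint, with the extension added to the full 4 weeks; that gives days 35–42. Both arguments limit the harm. Neither rescues the wording: item 2 does not describe a checkpoint, and a site should not have to infer a hold length from the surrounding items.

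Three stronger readings are tempting, and the documents do not support them.

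- **That 6.3 contradicts 4.8.3.** The list in 6.3 is permissive and applies whether or not 4.8.3 cites it. Its Medical Monitor approval concerns continuing therapy after a delay of more than 28 days; it is not a condition for keeping a subject on hold.
- **That misreading item 2 causes an irreversible stop.** The only withdrawals in this sequence are in item 4. Nothing in item 2 triggers permanent discontinuation, so it does not bring in the bar on retreatment in 6.3.
- **That subjects stopped early go unscored for hematologic DLT and distort escalation.** Cohorts can be as small as one subject (4.2.1) or three (4.2.2), which makes the worry understandable. But drug cessation naturally includes a permanent stop. A marrow 35–42 days after cessation also comes after the 28-day DLT window has closed. The dose-escalation committee sees non-DLT toxicities as well and may halt or de-escalate at any time (4.2.1). Ongoing adverse events and significant laboratory abnormalities are followed after treatment (8.5, 7.3.7). For subjects still on hold, a 42-day treatment delay without leukemia is a separate DLT with no cellularity requirement (4.2.5).

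**Conclusion.** The point holds for item 2 alone. Its initial period of 2 weeks conflicts with item 1 and gives days 21–28, which is 14 days short at each end of the days 35–42 in item 3. A 4-week start agrees with items 1, 3 and 4 and with both 42-day criteria in 4.2.5.

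Severity is minor. The error sits in an operative rule on dosing and DLT timing, but it affects only subjects held under the blasts-below-5% row, and the neighbouring items make the intended duration recoverable. Power, alpha and sample size do not depend on it. The conclusion assumes that items 1, 3 and 4 and 4.2.5 state the intended durations. Four places agreeing against one makes that the natural reading.

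The missing cross-reference to 6.3 and the unstated position of the marrow after a permanent stop are matters of clarity, not errors.

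**What to change.** In 4.8.3, blasts below 5%, item 2, change the initial 2 weeks to an initial 4 weeks. This is one figure; it costs nothing and changes no other rule.

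Two clarifications are optional:

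- Cross-refer 4.8.3 to 6.3, stating that resuming treatment after a delay of more than 28 days needs Medical Monitor approval. The wording should not make approval a condition of continuing the hold, because 6.3 does not say that. Keep the 4-week bullet in 6.3: it also covers Grade 4 subjects at 10,000 to under 25,000/mm3 without fever, sepsis or bleeding, for whom 4.8.3 lists no hold.
- State that drug cessation in item 3 includes a permanent stop, so that in Part 1 the day 35–42 marrow for hematologic DLT is still obtained. The examination is already specified, so the burden is at most one marrow in the few discontinued subjects to whom it applies.

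No additional subjects are needed.
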